2.2 Secondary Objectives

2.2.1 To prospectively characterize MCD presentation in Malawi.

2.2.2 To determine overall survival rate.

2.2.3 To determine event-free survival rate.

2.2.4 To describe the efficacy of the risk-adjusted treatment protocol as determined by clinical response rates at end of treatment and 12 weeks after start of treatment.

2.2.5 To describe radiologic response rates at end of treatment and 12 weeks after start of treatment.

2.2.6 To further characterize the safety by describing the frequency of all AEs with risk-adjusted treatment-protocol for MCD in Malawi.

2.2.7 To describe the rate of Kaposi sarcoma exacerbation, as defined by symptomatic or clinical (dermatologic or visceral organ) exacerbation of disease in patients receiving the risk-adjusted treatment protocol.

2.2.8 To describe the quality of life of patients with MCD before, during and after treatment with a rituximab-based, risk-adjusted treatment protocol, as assessed by the MCD symptom score and PROs.⁴²

2.2.9 To describe the trends in hemoglobin, platelet count, C-reactive protein (CRP), and IL-6 before, during, and after a risk-adjusted, rituximab-based treatment protocol

for MCD in Malawi and describe the utility of these markers as a predictor of relapse.

2.2.10 To evaluate for predictors of relapse or refractory disease with a risk-adjusted, rituximab-based treatment protocol.

2.2.11 To evaluate changes in Kaposi sarcoma viral load as a result of treatment.

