5.0 TREATMENT PLAN

5.1 Schema

[figure not shown]

Figure 4. Clinical trial schema for newly diagnosed patients with MCD requiring treatment.
"High-risk disease" defined as ECOG performance status >2 or hemoglobin <8 g/dL.

Clinical trial schema for newly diagnosed patients with MCD requiring treatment.

¹ "High-risk disease" defined as ECOG performance status >2 or hemoglobin <8 g/dL at the time of screening or enrollment labs. Note that a patient receiving a blood transfusion due to hemoglobin <8 g/dL within 1 month of enrollment will be considered high-risk.

² See Time and Events Table (8.1) for detailed study visit components.

³ MCD-SS=MCD symptom score

We will conduct a single arm, phase II clinical trial for safety and efficacy of risk-stratified treatment with rituximab +/- chemotherapy for MCD. Eligible patients will be enrolled and treated according to the study schema. High-risk patients (defined as patients with ECOG performance status >2 or hemoglobin <8 g/dL at the time of screening or enrollment labs)^{9,10,13-16} will receive four weekly doses of rituximab (375 mg/m²) and etoposide (100 mg/m²) as in Bower, et al.⁹ Low-risk patients will receive the same dose of rituximab alone.

The planned sample size is 27 patients and the primary outcome is safety. Secondary outcomes include one- and two-year EFS (combination of relapse, development of NHL, or death), OS, and KS exacerbation rates.

We will also collect clinical, laboratory, virologic data, and stored samples at baseline and end-of-treatment to both describe the presentation of MCD in our population and to evaluate risk factors for death or relapse.

Finally, we will conduct comprehensive microcosting analysis and a Markov model cost-effectiveness analysis.

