6.2.1 Adverse events associated with etoposide

The following data on adverse reactions are based on both oral and IV administration of etoposide as a single agent, using several different dose schedules for treatment of a wide variety of malignancies.

Hematologic Toxicity: Myelosuppression is dose related and dose limiting with granulocyte nadirs occurring 7 to 14 days after drug administration and platelet nadirs occurring 9 to 16 days after drug administration. Bone marrow recovery is usually complete by day 20, and no cumulative toxicity has been reported. The occurrence of acute leukemia with or without a preleukemic phase has been reported rarely in patients treated with etoposide in association with other antineoplastic agents.

Gastrointestinal Toxicity: Nausea and vomiting are the major gastrointestinal toxicities. The severity of such nausea and vomiting is generally mild to moderate with treatment discontinuation required in 1% of patients. Nausea and vomiting can usually be controlled with standard antiemetic therapy. Gastrointestinal toxicities are slightly more frequent after oral administration than after IV infusion.

Hypotension: Transient hypotension following rapid IV administration has been reported in 1% to 2% of patients. It has not been associated with cardiac toxicity or electrocardiographic changes. No delayed hypotension has been noted. To prevent this rare occurrence, it is recommended that etoposide be administered by slow IV infusion over a 30- to 60-minute period. If hypotension occurs, it usually responds to cessation of the infusion and administration of fluids or other supportive therapy

as appropriate. When restarting the infusion, a slower administration rate should be used.

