10.2 Sample Size, Accrual and Duration of Accrual

To assess safety, toxicities will be monitored, graded, and documented by investigators at each clinic visit. Rituximab-based treatment will be considered safe in this population provided <40% non-hematologic AEs; we hypothesize that the true rate will be around 20%, based on previous studies.^{9,10,15,16} With a sample size of 24 patients, we reach 80% power to reject (if we observe $\leq 6 \geq$ Grade 3 AEs) the null hypothesis (H_0 : toxicity rate $>40\%$) using a one-sided exact test at $\alpha=0.1$. To account for 10% possible loss to follow-up during the toxicity-monitoring period, we will plan to enroll 27 patients. We plan to enroll approximately 10 patients annually and therefore expect to accrue patients for a total of three years.

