10.5 Secondary Objectives

10.5.1 To better characterize MCD presentation in Malawi.

Basic demographics and baseline laboratory values will be summarized using descriptive statistics (i.e., means, medians, and variability measures for continuous variable; rates and proportions for binary variables).

10.5.2 To describe the efficacy of the risk-adjusted approach as determined by clinical and radiologic response rates, 90-day, one-year, and two-year EFS and OS.

An event for EFS is either relapse (defined as “MCD attack” in the Inclusion Criteria (section 4.1)), refractory disease, lost-to-follow-up (LTFU), or death. We will consider patients LTFU if they cannot be contacted by phone for three months. Given the high mortality associated with MCD and previously published literature supporting a strong association between LTFU and mortality in SSA, we will consider LTFU as a failure event for both EFS and OS.⁴³ Relapse for purposes of this study will be defined as recurrence of an “MCD attack” (Inclusion Criteria; section 4.1) requiring re-initiation of treatment, with a strong preference for biopsy-proven recurrence whenever possible. We will conduct survival analysis using Kaplan-Meier methods. Radiologic response will be assessed in parallel with clinical response with response criteria defined in section 7.1.7. We will assess the prognostic value of radiologic response for EFS and OS in Cox proportional hazards model.^{10,15,16}

10.5.3 To describe the safety, as determined by the rate of all AEs during a risk-adjusted approach to treatment of MCD in Malawi.

All AEs will be described up to 30 days after final dose of MCD-directed treatment.

10.5.4 To describe the rate of KS exacerbation, as defined by symptomatic or clinical (dermatologic or visceral organ) exacerbation of disease.

The rate of KS exacerbation will be reported as the number of KS cases requiring KS-specific treatment divided by the number of patients with pre-existing KS (as defined by personal history of KS, baseline presence of KS, or KS in lymph node biopsy). This will be estimated along with a 95% confidence interval for the proportion.

10.5.5 To describe the quality of life of patients with MCD before, during and after treatment with a rituximab-based, risk-adjusted treatment approach, as assessed by the MCD symptom score⁴² and PROPr instrument.⁴⁴

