The MCD symptom score will be summed and differences across treatment will be compared using a paired t-test. We hypothesize that quality of life will be significantly improved from baseline to end of treatment with rituximab-based treatment (the MCD symptom score will be lower and PRO-Pr will be higher in utility).

10.5.6 To describe the trends in hemoglobin, platelet count, CRP, IL-6, IL-10, and KSHV viral load before, during, and after treatment with a risk-adjusted, rituximab-based treatment for MCD in Malawi, and to describe the utility of these markers as a predictor of relapse.

Hemoglobin, platelet count, CRP, IL-6, IL-10, and KSHV viral load will be measured at baseline, day 15, and end-of-treatment. Differences will be compared by paired t-test. We hypothesize that hemoglobin, platelet count, CRP, and plasma KSHV viral load will be strongly associated with disease activity (hemoglobin and platelet count will increase in remission and CRP and KSHV viral load will decrease in remission).

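### Section 10.5.6 tests hemoglobin and platelet changes without a split by regimen, so the result mixes disease response with etoposide myelosuppression

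*Combined protocol and SAP*

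**What the plan says.** **Analysis.** Section 10.5.6 covers hemoglobin, platelet count, CRP, IL-6, IL-10 and KSHV viral load at baseline, day 15 and end of treatment. It gives one method: "Differences will be compared by paired t-test". It mentions neither risk group nor regimen. It then hypothesizes that hemoglobin, platelets, CRP and plasma KSHV load track disease activity, with hemoglobin and platelets rising in remission. The matching objective, 2.2.9, begins "To describe the trends in hemoglobin, platelet count, C-reactive protein (CRP), and IL-6 before, during, and after a risk-adjusted, rituximab-based treatment protocol" and also asks whether the markers are useful for predicting relapse.

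**Regimen.** High-risk disease is "defined as ECOG performance status >2 or hemoglobin <8 g/dL at the time of screening or enrollment labs" (5.1). Where a patient was transfused, the pre-transfusion hemoglobin decides the group (5.1 footnote 1, Table 7 footnote 15, 10.1). High-risk patients receive rituximab plus etoposide on days 1, 8, 15 and 22. Low-risk patients receive rituximab alone (Table 1, 10.1).

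**Etoposide and blood counts.** Section 1.4 names anemia and thrombocytopenia among the common adverse events. Section 6.2.1 (Adverse events associated with etoposide) describes "platelet nadirs occurring 9 to 16 days after drug administration" and says that marrow recovery is usually complete by day 20.

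**Visits and transfusion.** The end-of-treatment visit falls 7 to 14 days after the final dose (Table 7 footnote 3). Transfusion is generally recommended below 7 g/dL on etoposide and below 6 g/dL on rituximab alone, with provider discretion as the main driver (5.4.2). A CBC is also scheduled at 12 weeks and at each long-term follow-up visit (Table 7).

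**The concern.** The paired t-test uses time point only and does not use remission status. Reading a change as disease activity therefore rests on the change itself. For hemoglobin and platelets, that change has a second source in one group only.

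An etoposide patient whose disease is responding may show a flat or falling platelet count because the sample was taken at the drug's nadir. A rituximab-only patient with the same response would show a rise. Averaged together, the two can hide the rise that the hypothesis expects, and the size of the average depends on how many high-risk patients happen to enroll. Transfusion guidance that differs by regimen adds a further difference for hemoglobin.

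At stake is a secondary conclusion on whether inexpensive blood counts can follow disease activity. The primary safety analysis is not affected.

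**Working it through.** **1. The plan's own figure.** The plan gives no precision or power figure for the marker analyses. Its only sample-size statement, "With a sample size of 24 patients, we reach 80% power to reject", concerns the primary safety test, and it reproduces:
- P(X ≤ 6 | n = 24, p = 0.40) = 0.096, below the stated 0.1.
- P(X ≤ 6 | n = 24, p = 0.20) = 0.811, against the stated 80%.
- 24 / 0.9 = 26.7, so 27 enrolled.

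The number available for the markers is thus at most about 27.

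**2. Do the samples fall in the platelet nadir?** Window = dose day + 9 to dose day + 16 (Table 1; 6.2.1).

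| Dose day | Nadir window (study days) |
|---|---|
| 1 | 10–17 |
| 8 | 17–24 |
| 15 | 24–31 |
| 22 | 31–38 |

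- Day 15 lies in the first window.
- End of treatment is 22 + 7 to 22 + 14 = days 29–36, inside the third and fourth windows.

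On schedule, both post-baseline platelet samples of an etoposide patient lie in a nadir window. The windows join up over days 10–38. The ±7-day visit allowance can therefore move a sample out only at the edges (days 8–9, or after day 38), although held doses would shift the windows. The documents give no nadir timing for hemoglobin.

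**3. When is the drug effect over?** Last dose on day 22 plus 20 days for recovery gives day 42. The 12-week visit is at about day 84, well beyond that.

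**4. How common is the platelet effect?** Table 6 reports platelets below 100,000/mm³ in 22–41% of patients on single-agent etoposide, across mixed schedules and cancers, and anemia in 0–33%. The documents do not give the etoposide share. Assuming 20–60% of 27, that is 5 to 16 patients, and 5 × 0.22 = 1.1 to 16 × 0.41 = 6.6. So roughly 1 to 7 patients might be affected, if those rates carry over.

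**5. How far does the pooled mean move with the mix?** Pooled change = f·dH + (1 − f)·dL, where f is the etoposide share. Assume dL = +2 g/dL hemoglobin on rituximab alone and vary dH, the change with etoposide. None of these changes is in the documents.

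| dH (g/dL) | f = 0.2 | f = 0.4 | f = 0.6 |
|---|---|---|---|
| −1 | 1.4 | 0.8 | 0.2 |
| 0 | 1.6 | 1.2 | 0.8 |
| +1 | 1.8 | 1.6 | 1.4 |
| +3 | 2.2 | 2.4 | 2.6 |

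Reading across a row, nothing changes within either group, yet the pooled figure moves. The movement is large only where the two groups differ markedly.

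**6. What does splitting cost?** The 95% half-width for a mean paired change, in SDs of the change, is t(0.975, n − 1)/√n.
- Pooled, n = 27: 0.40.
- Etoposide group, n = 5 to 16: 1.24 to 0.53.
- Rituximab-only group, n = 22 to 11: 0.44 to 0.67.

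**7. Hemoglobin as a relapse predictor.** Below 8 g/dL no patient is assigned rituximab alone, so across that line hemoglobin and regimen cannot be separated. Applying the one-year EFS values of 92% and 71% (1.3) and 78% (1.5) to 27 patients gives 27 × 0.08 = 2.2, 27 × 0.29 = 7.8 and 27 × 0.22 = 5.9 events. That is too few to support a model with several terms.

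**The case against.** **The pooled change answers the objective.** Objective 2.2.9 is to describe trends under a risk-adjusted strategy, and each patient serves as his or her own control. This stands. The pooled change is a valid description of the strategy, and pooling two trajectories does not confound a between-group comparison. What does not follow is the reading in 10.5.6 of a hemoglobin or platelet change as disease activity.

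**The evidence is uneven.** The nadir figures concern granulocytes and platelets, anemia is listed at 0–33%, transfusion is mainly at provider discretion, and later CBCs fall after marrow recovery. All of this stands. The platelet case is the stronger one. The later CBCs help, but 10.5.6 names only the three early time points.

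**A stronger reading does not hold.** A reader might infer that relapse-predictor analyses are pooled as well, and that hemoglobin's prognostic effect would be biased by a calculable amount. The documents do not support this:
- Objective 2.2.10 is "To evaluate for predictors of relapse or refractory disease with a risk-adjusted, rituximab-based treatment protocol", but the readable text gives no method for it. Section 10.6 is redacted, so nothing can be concluded about what it contains.
- The Cox model in 10.5.2 concerns something else: "We will assess the prognostic value of radiologic response for EFS and OS in Cox proportional hazards model".
- Section 1.3 says that adding etoposide lowers the risk of death. It gives no effect on relapse, so any relapse hazard ratio for etoposide would be invented.
- Stratifying by risk group is not a clean remedy. With ECOG above 3 excluded (4.2.10), every high-risk patient with hemoglobin of 8 g/dL or more is there because of ECOG 3. Within that group, hemoglobin is therefore tied to performance status by the selection rule itself.

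**Conclusion.** The point holds for hemoglobin and platelet count in 10.5.6. As written, the analysis can show how counts moved under the whole strategy. It cannot show whether that movement reflects disease response, because etoposide patients are sampled twice within the drug's platelet nadir and rituximab-only patients have no such nadir.

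The size cannot be fixed from the documents, which give neither the etoposide share nor mean changes by regimen. Under the assumed changes, raising the share from 20% to 60% moves the pooled hemoglobin change from 1.4 to 0.2 g/dL in the most divergent case. Where the etoposide group gains 1 g/dL, it moves only from 1.8 to 1.4 g/dL.

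Two further inferences are not supported. Nothing in the documents shows a comparable etoposide effect on CRP, IL-6, IL-10 or KSHV load. Nor do they say that half the patients will receive etoposide. This is a worthwhile change to how a secondary result is reported. It leaves the design, the sample size and the primary test as they are.

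**What to change.** In section 10.5.6:

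1. Keep the pooled paired comparison as the description of the strategy. Beside it, report hemoglobin and platelet changes with confidence intervals separately for the rituximab-only and the rituximab-plus-etoposide patients.
2. Flag hemoglobin and platelet values that follow a transfusion.
3. Base any statement about disease activity on the by-regimen results, supported by the CBCs already scheduled at 12 weeks and in long-term follow-up.
4. Present the two groups as descriptions and not as a comparison of regimens, since hemoglobin and performance status formed them.
5. If hemoglobin is examined as a relapse predictor, state that across 8 g/dL it cannot be separated from regimen. A stratified Cox model should not be required with about 27 patients.

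The cost is a few sentences in the analysis plan and wider by-group intervals, especially if few patients receive etoposide. Risk group, transfusions (as recorded concurrent therapy, 7.1.1) and CBCs are already part of the planned data, so no visits, samples or patients are added.

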2.3 Exploratory Objectives

2.3.1

[REDACTED]

[REDACTED]

[REDACTED]

3.0 STUDY ENDPOINTS

3.1 Primary Endpoint

Safety will be classified and graded by non-hematologic Grade ≥ 3 AEs (CTCAE v5.0) and treatment-related mortality through twelve weeks from the start of rituximab with or without etoposide therapy.

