Tumor Lysis Syndrome: Rituximab rapidly decreases benign and malignant CD20 positive cells. Tumor lysis syndrome has been reported to occur within 12 to 24 hours after the first rituximab infusion in patients with high numbers of circulating malignant lymphocytes. Patients with high tumor burden (bulky lesions) may also be at risk. Patients at risk for developing tumor lysis syndrome should be followed closely and appropriate laboratory monitoring performed.

Hepatitis B Reactivation with Related Fulminant Hepatitis and Other Viral Infections: Hepatitis B virus (HBV) reactivation with fulminant hepatitis, hepatic failure, and death has been reported in some patients with hematologic malignancies treated with rituximab. The majority of patients received rituximab in combination with chemotherapy. The median time to diagnosis of hepatitis was approximately four months after the initiation of rituximab and approximately one month after the last dose. Persons at high risk of HBV infection should be screened before initiation of rituximab. Carriers of hepatitis B should be closely monitored for clinical and laboratory signs of active HBV infection and for signs of hepatitis during and for up to several months following rituximab therapy. In patients who develop viral hepatitis, rituximab and any concomitant chemotherapy should be discontinued and appropriate treatment, including antiviral therapy, initiated. There are insufficient data regarding the safety of resuming rituximab therapy in patients who develop hepatitis subsequent to HBV reactivation. The following additional serious viral infections, either new, reactivated or exacerbated, have been identified

in clinical studies or postmarketing reports. The majority of patients received rituximab in combination with chemotherapy or as part of a hematopoietic stem cell transplant. These viral infections included John Cunningham virus, which is associated with progressive multifocal leukoencephalopathy, cytomegalovirus, herpes simplex virus, parvovirus B19, varicella zoster virus, West Nile virus, and hepatitis C. In some cases, the viral infections occurred up to one year following discontinuation of rituximab and have resulted in death.

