8.0 EVALUATIONS AND ASSESSMENTS

8.1 Time and Events Table (Table 7)

Table 7: Time and Events Table.	Initial Visit or Relapse ¹	Treatment days 1, 8, 15, and 22 ²	End-of-treatment (Week 5)	Follow-up (12 weeks)	Long term follow up ⁴
Informed consent	Initial visit only				
History & physical exam ⁵	X	X	X	X	X
Concomitant medications ⁶	X	X	X		
ECOG performance status ⁷	X	X	X		
Toxicity evaluation ⁸	X	X	X	X	X ⁸
Tumor biopsy ⁹	X				
Survival ¹⁰		X	X	X	X
Treatments ¹¹		X			
Lymph node measurements	X	Day 15 only	X	X	X
MCD-SS and Quality of life assessment ¹²	X	Day 15 only	X	X	X ¹²
Chest X-ray and abdominal ultrasound	X		X ¹³		
Hematology & blood chemistries ¹⁴	X ¹⁵	X ¹⁶	X	CBC only	CBC only
Correlative blood samples ¹⁷	X	Day 15 only	X	X	X ¹⁹
Lactate dehydrogenase	X	Day 15 only	X		

Viral and host genotyping	X	
Urine pregnancy test	X ¹⁸	
Hepatitis B (for HIV-negative patients)	X	
CD4 and HIV RNA (if HIV positive)	X	X ¹⁹

¹ Screening assessments must be completed within 21 days prior to study enrollment.

² A window of +/- 7 days will apply to all study visits; however, lymph node measurements must take place prior to that cycle's treatment.

³ End-of-treatment visit should occur 7-14 days from final dose of chemotherapy. A subject who is being withdrawn for disease progression or for other reasons (e.g. unacceptable toxicity, etc.) should complete an end of treatment visit.

⁴ Long term follow-up will occur every 3 months until 24 months after the start of treatment unless otherwise noted.

⁵ After the initial visit (comprehensive history and physical exam) subsequent visits will address a focused history and physical exam.

⁶ All concomitant medications will be recorded.

⁷ See Appendix E. ECOG Performance Status

⁸ per NCI CTCAEv5.0 for notation of baseline toxicity. Assess from initial visit through first follow-up visit (12 weeks) and again at the final follow up visit (24 months).

⁹ Archival and/or fresh sample.

¹⁰ Survival will be assessed at each visit through out the duration of treatment, follow up, and long term follow up.

¹¹ Subjects with low risk disease will receive rituximab at 375 mg/m² weekly for 4 weeks. High risk subjects will receive rituximab at 375 mg/m² and etoposide at 100 mg/m² weekly for 4 weeks.

¹² Quality of life assessment includes PROMIS Global 10, MCD-SS and QoL will be assessed through follow up, and at 24 months during long term follow up. QoL will also be assessed at the time of any relapse.

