¹³ Omitted if no baseline abnormalities on chest x-ray and abdominal ultrasound.

¹⁴ Hematology assessments include hemoglobin, white blood cell count, white blood cell differential, and platelet count. Blood chemistry assessments include serum creatinine, total bilirubin, albumin, and the following as deemed necessary per SOC: sodium, potassium, chloride, bicarbonate, glucose, blood urea nitrogen, aspartate aminotransferase, alanine aminotransferase, and alkaline phosphatase. See the T&E table for when lactate dehydrogenase is measured.

¹⁵ If a patient has been tested for hemoglobin within 1 month of enrollment and received a blood transfusion due to low hemoglobin, then the original test will dictate treatment group (high vs low risk).

¹⁶ Hemoglobin and platelet count will be assessed per SOC during treatment.

¹⁷ Blood sample for correlates will include assessments of C-reactive protein, KSHV viral load from plasma and PBMCs, and cytokine levels (IL-6, IL-10, IL-2, TNF α , INF γ). KSHC genotyping will occur on the first draw only. Blood draws will be two 10 mL tubes (2 heparin tubes separated into plasma and PBMCs) and 1 tube (5 mL) with citrate. Correlative blood samples collected during long term follow up will be stored and analyzed

¹⁸ In women under 60 years of age, required within 3 days of start of treatment.

¹⁹ At 12 and 24 month long term follow up visits.

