9.0 ADVERSE EVENTS

9.1 Definitions

9.1.1 Adverse Event (AE)

An adverse event (AE) is any untoward medical occurrence (e.g., an abnormal laboratory finding, symptom, or disease temporally associated with the use of a drug) in a subject or clinical investigation subject administered an investigational product and which does not necessarily have a causal relationship with this treatment. An AE can therefore be any unfavorable and unintended sign, including an abnormal laboratory finding, symptom, or disease temporally associated with the use of a medicinal product, whether or not related to the medicinal product.

Hospitalization for elective surgery or routine clinical procedures that are not the result of an AE (e.g., surgical insertion of a central line) need not be considered AEs and should not be recorded as such. Disease progression should not be recorded as an AE unless the investigator deems it attributable to the study therapy.

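### The primary safety endpoint runs to 12 weeks, but no blood chemistry is scheduled after week 5 and liver enzymes and electrolytes are never scheduled, so silent laboratory events may go uncounted

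*Combined protocol and SAP*

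**What the plan says.** Section 3.1 sets the primary endpoint: "Safety will be classified and graded by non-hematologic Grade ≥ 3 AEs (CTCAE v5.0) and treatment-related mortality through twelve weeks", counted from the start of rituximab with or without etoposide. Section 9.1.1 defines an adverse event broadly, as "any unfavorable and unintended sign, including an abnormal laboratory finding, symptom, or disease temporally associated with the use of a medicinal product". A Grade ≥3 creatinine, bilirubin, transaminase or electrolyte value can therefore be a qualifying event without any symptom.

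Table 7 (Section 8.1) sets what is measured. Its combined hematology and chemistry row is marked at the initial visit or relapse, on treatment days and at end of treatment. At the 12-week and long-term visits it is cut to a blood count. No visit lies between end of treatment and week 12.

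Footnote 14 defines the fixed panel: "Blood chemistry assessments include serum creatinine, total bilirubin, albumin". It then adds "and the following as deemed necessary per SOC: sodium, potassium, chloride, bicarbonate, glucose, blood urea nitrogen, aspartate aminotransferase, alanine aminotransferase, and alkaline phosphatase". Section 7.2.2 makes the same division. Liver enzymes and electrolytes are thus not fixed tests at any visit, baseline included.

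Table 7 does schedule a history, an examination and a CTCAE toxicity evaluation at 12 weeks. Sections 9.2 and 9.3.1, however, end the recording of adverse events and serious adverse events 30 days after treatment is discontinued.

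**The concern.** The endpoint window and the laboratory schedule do not match. A site that follows Table 7 exactly has no planned means of seeing an asymptomatic renal or hepatic abnormality between week 5 and week 12. It has no planned means of seeing a silent transaminase or electrolyte abnormality at any time.

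The possible error runs one way. An event that is never measured can only lower the count, and a lower count favours declaring the regimen safe. Safety is the primary outcome, and the trial is justified by the lack of regional safety data, so incomplete ascertainment bears directly on the main conclusion. The adverse-event boundary in Table 8 monitors the same type of event and would be affected in the same direction.

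**Working it through.** **1. Reproduce the design (Section 10.2).** Inputs: n = 24; safety is declared if 6 or fewer events are seen; null rate 40%; expected rate 20%; one-sided exact test at 0.1; 10% loss to follow-up. I take X as the number of patients with at least one qualifying event.

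P(X ≤ 6) = Σ (k = 0 to 6) C(24, k) p^k (1 − p)^(24 − k)

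- p = 0.40: 0.096, within the 0.1 limit.
- p = 0.20: 0.811, matching the stated 80% power.
- Enrolment: 24 / 0.9 = 26.7, rounded up to 27.

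The design reproduces. The margin below nominal alpha is only 0.100 − 0.096 = 0.004.

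**2. Length of the gap.** The last dose is on day 22 (Table 1). The end-of-treatment visit is 7 to 14 days later (Table 7 footnotes), so day 29 to 36. The window closes at 12 × 7 = day 84.

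- Day 29: (84 − 29) / 84 = 55/84 = 65%.
- Day 36: (84 − 36) / 84 = 48/84 = 57%.

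These are nominal. The ±7-day visit window and held doses would move them. For liver enzymes and electrolytes the gap is the whole window.

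**3. Recording limit.** 22 + 30 = day 52, which is 84 − 52 = 32 days before the endpoint closes. As Sections 9.2 and 9.3.1 stand, a laboratory event found at week 12 falls outside the recording period.

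**4. Sensitivity to missed events.** Let d be the proportion of all patients whose only qualifying event is an unseen laboratory abnormality. A patient who also has another Grade ≥3 non-hematologic event is counted anyway and does not contribute to d. The observed rate is 0.40 − d. The values of d are assumptions.

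| d (assumed) | Share of affected patients, d / 0.40 | Observed rate | P(X ≤ 6) |
|---|---|---|---|
| 0 | 0 | 0.40 | 0.096 |
| 0.01 | 2.5% | 0.39 | 0.114 |
| 0.03 | 7.5% | 0.37 | 0.157 |
| 0.05 | 12.5% | 0.35 | 0.211 |
| 0.10 | 25% | 0.30 | 0.389 |

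One percentage point is enough to pass the nominal 0.1. The last row needs one affected patient in four to have had nothing but a silent laboratory event. It is shown only to mark the range.

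**The case against.** The strongest reply is that the plan already looks for what matters clinically. Week 12 has a history, an examination and a CTCAE evaluation. Section 7.1.5 adds patient-reported events through PRO-CTCAE. Chemistry can be ordered when indicated, and the initial-visit column, chemistries included, also applies at relapse. In a resource-limited setting, clinically triggered chemistry after treatment is a defensible choice. Keeping the blood count at week 12 also has its own purpose, since anemia and thrombocytopenia are among the flare criteria in Section 4.1.7 that define relapse. All of this stands, and it limits the point to asymptomatic laboratory events.

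A reader might infer that the rate is shown to be biased low. The documents do not support that, because they give no frequency for silent Grade ≥3 laboratory events. The nearest figure is hepatic toxicity of 0–3% in Table 6. It is not limited to Grade ≥3 or to silent events and concerns etoposide alone, which only high-risk patients receive. It lends no support to values of 5–10%.

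A reader might also take Section 6.1.6 as evidence that such events are expected in the gap. The support is thin:

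- **Renal toxicity** is tied there to tumor lysis or concomitant cisplatin. Tumor lysis is placed 12 to 24 hours after the first infusion, and cisplatin is not in the regimen.
- **Hepatitis B reactivation:** "The median time to diagnosis of hepatitis was approximately four months after the initiation of rituximab" puts the median at about day 120 (4 × 30), after the window closes. The same sentence also gives about one month after the last dose, roughly day 52, which is inside it. The text can be read either way.
- **Mitigation:** HIV-infected patients must be on or willing to start lamivudine or tenofovir, and HIV-negative patients are tested for surface antigen. This lowers the hepatitis B risk but supplies no measurement after week 5.

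Finally, the Table 8 boundaries are stated to be non-binding, and the effect on them has not been quantified.

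**Conclusion.** The mismatch is real and follows from the text alone. Laboratory abnormalities count towards a 12-week endpoint, but creatinine and bilirubin are not scheduled in the last 57–65% of the window, and liver enzymes and electrolytes are not scheduled at all. Laboratory-only events are therefore not systematically ascertained, and the safety rate may be underestimated. The direction is certain; the amount is unknown.

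The rise from 0.096 to 0.16–0.21 holds only under the assumption that 3–5% of patients have such an event as their sole qualifying event, at a true rate of 40%. It shows how little slack the decision rule has and is not an estimate of the actual error. The design calculation itself is sound. The point deserves an amendment because safety is the primary outcome and the correction is cheap.

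**What to change.** - **Table 7, 12-week visit:** replace the blood count alone with a blood count plus creatinine, total bilirubin and AST/ALT. Add electrolytes if electrolyte abnormalities are meant to count. Blood is already drawn at this visit for the count and the correlative samples.
- **Footnote 14 and Section 7.2.2:** make AST/ALT required at baseline, end of treatment and week 12, so that a later abnormality can be told from one present at entry.
- **Sections 9.2 and 9.3.1:** reconcile the 30-day recording limit with the 12-week endpoint in Section 3.1 and the 12-week toxicity evaluation in Table 7. Without this, a week-12 result has no place in the recording period.
- **Sections 3.1 and 10.4.1:** state that transient silent events between week 5 and week 12 are seen only when chemistry is clinically triggered. A single panel at day 84 does not cover the whole interval.

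Cost: about 27 extra chemistry panels (one per enrolled patient) and at most 2 × 27 = 54 AST/ALT measurements on draws already scheduled. The observed adverse-event rate may come out slightly higher. Sample size, the cut-off of 6, alpha and power stay as they are. If the sponsor prefers not to add tests, the minimum is to state that laboratory-only events are ascertained only when clinically triggered and to report the rate with that limitation.
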